**Figure 2. Study Schema**

## 2.0 OBJECTIVES AND SCIENTIFIC AIMS

Aim 1. Determine the **usability and feasibility** of HN-STAR.

We will evaluate the components of HN-STAR in two parts. In Aim 1: Part 1, survivors at MSK (N=10) and their nurse practitioner (N=1) will provide in-depth feedback on the usability of HN-STAR.

After refining HN-STAR, Aim 1: Part 2 will elicit feedback from survivors at MSK (N=30) and Hartford HealthCare (N=15) and the survivors' primary care providers (N=45) regarding feasibility of HN-STAR in clinical practice. The nurse practitioners (N=2) will provide in-depth feedback on the usability of HN-STAR.

Aim 2. Assess **preliminary metrics** of HN-STAR use in preparation for a multi-site randomized controlled trial.

Using data from survivors in Aim 1: Part 2 (N=45), we will abstract data on health care actions from both the medical record and HN-STAR. Such data include receipt of appropriate oncologic surveillance, identification and management of symptoms, and appropriate preventive health services, as indicated by referrals, prescriptions, and recommendations in both clinic notes and the HN-STAR Survivor Self-Assessment. This Aim will determine the feasibility of data collection, establish baseline health status measures, and contribute to power calculations for the future trial.

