2. *Symptom algorithms* use PRO-CTCAE responses to identify toxicities of treatment and other relevant issues to address. In the Interactive Discussion Guide, seen only by the NP, these symptoms populate an evidence-based list of common diagnosis to consider evaluation and management options. We have developed these recommendations based on existing evidence when available and institutional consensus within MSK and approval from HH otherwise. We will refine these guidelines as new evidence emerges.
3. *Prevention algorithms* use patient responses and demographic information to generate a list of personalized prevention recommendations, based on guidelines from the United States Preventive Service Task Force and the NCCN survivorship guidelines. Using the Interactive Discussion Guide, the NP will discuss ongoing care and select management plans with the survivor. Selected symptom management plans are entered into HN-STAR and populate the Survivorship Care Plan (described below).

None of the patients will see the Interactive Discussion Guide, which is intended only for the NP to use during the clinic visit. An example of content of Interactive Discussion Guide is shown below in Figure 3. The NP at each site will be trained on how to use the Interactive Discussion Guide.

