**Physical exam**

- Assess for increased neck size or obesity indicating possible causes of sleep apnea

**Recommendations for evaluation and management** (Check all that apply.)

- Referral to primary care provider
- Sleep log
- Sleep hygiene review (routine of bed time and awakening, light exposure, avoiding naps, and only being in bed to sleep)
- Consider discontinuing or reducing use of steroids, opioids, anti-depressants.
- Physical activity (moderate aerobic exercise for 2.5 hours a week and strength training 2-3 days a week)
- Referral to psychology (MSK)
- Referral to psychology (outside)
- Referral to integrative medicine (MSK)
- Prescription for sleep aide
- Patient education material on sleep
- Video on sleep
- Not discussed because chronic and previously addressed
- Other (Note names of providers or other details not described above)

**4.2.4** Finally, the **Survivorship Care Plan** will present a treatment summary and plan of care. HN-STAR generates a Survivorship Care Plan after each visit (See template in Appendix C). The treatment summary contains a plain-language cancer history. The plan of care contains personalized recommendations for cancer surveillance, management of late effects, and preventive care. It also reports a list of non-cancer conditions reported by the patient. Each recommendation includes a schedule and clear delineation of who is responsible. The plan of care also contains generic survivorship information, with a description of signs and symptoms to report to the oncology provider, contact information for the oncology provider, and recommendations to visit a primary care provider.

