**11.3.1 Oncologic outcomes.** We will only investigate late effects that we assess in HN-STAR. (If usability testing identifies additional late effects we did not target in our Survivor Self-Assessment, we will add them to the Survivor Self-Assessment for Aim 1: Part 2 and include them in Appendix H.) For each late effect, we will consider it identified if it was mentioned in a clinic note, and we will consider it addressed if there was a referral,

recommendation, education, or explicit acknowledgement of inaction. (Inaction may be appropriate, because in some cases, when symptoms are persistent and intractable, no intervention may be recommended.) For each patient, we will first count the number of late effects identified. We will then calculate the proportion of identified late effects that are addressed.

We will use descriptive statistics to report each element of oncologic care listed in Appendix H (i.e. smoking cessation, dental exam, blood work for thyroid studies, endoscopic exam, and head and neck physical exam). Each patient may not require every element of follow-up, depending on their primary tumor site or treatment received. We will use the number of recommended elements of care as the denominator, and we will calculate the proportion of these elements that are performed.

**11.3.2 Non-oncologic outcomes.** The non-oncologic outcomes in HN-STAR are collected only once. They include cancer screening, vaccination, and other preventive care elements that are explicitly collected in the Survivor Self-Assessment. Only some of these elements will be recommended for each patient, depending on their age, sex, and behaviors. We will calculate the proportion of recommended elements of non-oncologic care that are performed per patient. In addition, for each element of non-oncologic care, we will calculate the proportion of patients who receive it as recommended.

Findings from Aim 2 will inform whether these metrics can be collected from the EMR and HN-STAR. In addition, they will inform the statistical analysis for the future trial. For oncologic metrics only (Section 9.0, Figure 4), we will calculate the difference before HN-STAR use and after. Differences in oncologic metrics will be used in the power calculation for the proposed randomized trial. Non-oncologic metrics will be reported descriptively to inform the feasibility of collecting these data from self-report.

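### The addressed proportion pools acknowledged inaction with active management, so its before-after change may mix an HN-STAR documentation effect with a change in care

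*Combined protocol and SAP*

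**What the plan says.** Section 11.3.1 sets the denominator by a low bar: for each late effect, "we will consider it identified if it was mentioned in a clinic note". The numerator accepts a referral or "recommendation, education, or explicit acknowledgement of inaction", with no distinction between them. The plan explains the last item: "Inaction may be appropriate, because in some cases, when symptoms are persistent and intractable, no intervention may be recommended". The per-patient statistic follows: "We will then calculate the proportion of identified late effects that are addressed".

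The excerpt of the Interactive Discussion Guide in Figure 3 (insomnia) includes, among its management tick boxes, "Not discussed because chronic and previously addressed". On where the ticks go, Section 4.2.3 says: "Selected symptom management plans are entered into HN-STAR and populate the Survivorship Care Plan".

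Section 11.3 and Figure 4 in Section 9.0 take the oncologic metrics from clinic notes; Figure 4 adds prescriptions and referrals. The pretest covers a year of notes and the posttest covers the one HN-STAR visit. Section 7.3.4 has the NP write that visit's note as routine care. The last paragraph of Section 11.3.2 gives the use of the result: "Differences in oncologic metrics will be used in the power calculation for the proposed randomized trial".

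**The concern.** One component of the numerator may be ascertained differently in the two periods because of the intervention itself. Before HN-STAR, a clinician who chose to leave a chronic symptom alone had to record that unprompted for it to count. At the HN-STAR visit, the NP works through a guide that offers a no-action entry, at least for insomnia, and then writes the note from which the outcome is abstracted. If the guide leads the NP to write down decisions that previously went unrecorded, the addressed proportion rises without any further referral, recommendation or education.

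A single pooled figure cannot separate that rise from a real one. This matters because the difference is carried into the sizing of a randomized trial whose primary outcomes, according to Section 3.0, include a count of late effects managed.

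**Working it through.** The plan gives no expected addressed proportion, effect size, alpha or power, so there is no figure to reproduce. The check has four steps. All values of p and f below are assumptions.

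**1. Can a tick count as evidence?** Read alone, the Aim 2 sentence in Section 2.0 seems to allow it: "we will abstract data on health care actions from both the medical record and HN-STAR". The next sentence of that section, however, names the HN-STAR source as the Survivor Self-Assessment, which the patient completes. Sections 9.0 and 11.3 place late effects in the clinic record. No section says that guide selections are copied into the note. The route that remains open is indirect: the same NP uses the guide and writes the note.

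**2. Size of a pure documentation effect.** Let p be the addressed proportion before, and f the share of identified but unaddressed effects that gain a recorded acknowledgement of inaction. Hold the set of identified effects and all active management fixed. Then:

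proportion after = p + (1 − p)f, so shift = (1 − p)f.

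| p | f = 0.10 | f = 0.25 | f = 0.50 |
|---|---|---|---|
| 0.40 | 0.60 × 0.10 = 6 points | 15 points | 30 points |
| 0.60 | 0.40 × 0.10 = 4 points | 10 points | 20 points |
| 0.80 | 0.20 × 0.10 = 2 points | 5 points | 10 points |

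If only active management is counted, the same scenario gives a shift of 0 by construction.

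**3. Direction.** The tool may also identify more late effects, which enlarges the denominator. Suppose 3 of 5 effects are addressed before (0.60) and two more are identified at the HN-STAR visit:

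- no recorded inaction: 3/7 = 0.43
- one recorded inaction: 4/7 = 0.57
- two recorded inactions: 5/7 = 0.71

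Active management is the same in all three cases, yet the pooled proportion can fall or rise.

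**4. Consequence for planning.** Suppose active management really moves from 0.60 to 0.70, and a share f of the remaining 0.30 gains recorded inaction. The apparent posttest value is 0.70 + 0.30f. The sample size is for two independent proportions, two-sided 0.05, 80% power, individual level and no clustering:

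| f | Apparent posttest value | n per arm | Power for the real 0.60 to 0.70 |
|---|---|---|---|
| 0 | 0.70 | 356 | 80% |
| 0.10 | 0.73 | 206 | 57% |
| 0.25 | 0.775 | 109 | 34% |
| 0.50 | 0.85 | 49 | 18% |

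These sizes show sensitivity only. The future trial randomizes clinics, and its stated outcomes are counts, so they are not estimates for that trial.

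**The case against.** The strongest reply is that the tick box has no stated path into the outcome. Ticks populate the Survivorship Care Plan, and the outcome comes from notes. A reader might infer that HN-STAR raises the addressed proportion directly through its own box; the documents do not support that. This part of the objection stands.

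The box also says that a topic was not discussed because it had been addressed before. No section states that this meets the definition of acknowledged inaction. If the earlier action is in a note from the pretest year, that effect already counts as addressed at pretest and adds nothing to the apparent gain. This limits how large f could plausibly be.

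The box can be seen for insomnia only. The full guide (Appendix M) and the abstraction form (Appendix H) are not in the text available, so its presence for other symptoms cannot be checked. Appendix H may already separate types of action.

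Counting inaction is a reasoned choice, and replacing the pooled figure with active management alone could bias the comparison the other way. A chronic symptom managed at any time in the pretest year would count before, while a justified decision to leave it alone at the single posttest visit would count as a failure. This also stands, and it is why the pooled figure should not simply be dropped.

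Finally, Section 11.1 makes this a descriptive study without formal tests. That limits the consequence to planning the next trial but does not remove it, because the plan commits the difference to that use.

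**Conclusion.** The point holds in a limited form. The plan pools two kinds of evidence, the intervention visibly prompts an entry resembling one of them, and the same NP writes the posttest note. The before-after change in the addressed proportion therefore cannot be read as a change in care alone.

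The documents do not establish that the change is inflated. The transfer of ticks to the note is not shown, and the net direction is open. Nor do they support the inference that inaction should not count at all.

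With care and identification unchanged, the possible shift across the assumed values runs from 2 points (p = 0.80, f = 0.10) to 30 points (p = 0.40, f = 0.50). No result of the present study becomes invalid. What is at risk is the planning input for the randomized trial, which could be too optimistic if a documentation effect dominates.

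**What to change.** - In Section 11.3.1 and Appendix H, code each identified late effect, in both periods, as (a) referral, recommendation or education, (b) acknowledged inaction only, or neither.
- Report the before-after difference for (a) and for (a) + (b), and carry both into the power calculation as a range.
- State that a Discussion Guide selection is not evidence unless it is also written in the clinic note, and say whether the box in Figure 3, if so written, falls under (b).

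The cost is one code on the abstraction form, one more row in a descriptive table and a sentence or two in Section 11.3.1. Category (a) alone leaves out appropriate inaction, so the plan's pooled figure stays beside it. The split should be in place before abstraction starts, because recovering it later would mean going back to the charts.

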We developed a web-based, algorithm-driven platform called the **Head and Neck Survivorship Tool: Assessment and Recommendations (HN-STAR)** to address the most salient issues in providing comprehensive survivorship care to head and neck cancer survivors. First, HN-STAR ensures the identification of all late effects by collecting symptom data directly from patients. It then synthesizes patient-reported outcomes, treatment data, and current evidence about survivorship care into a tailored Interactive Discussion Guide. The oncology provider uses the Interactive Discussion Guide in a routine oncology follow-up visit to address all elements of

comprehensive survivorship care. Finally, HN-STAR automatically creates the Survivorship Care Plan based on the clinic visit, which minimizes burden for oncology providers. This Survivorship Care Plan is updated at each visit to incorporate symptom changes, modified management plans, and more current evidence regarding survivorship care.

**The goal of our proposal is to evaluate the feasibility of HN-STAR in the setting of survivorship clinics, in preparation for a future multi-site randomized controlled trial.** The future trial will randomize clinics at multiple centers to use HN-STAR or usual care, and the primary outcomes will be changes in 1) the number of late effects identified and 2) the number of late effects managed in clinic. We will also investigate adherence to recommended care and any changes in health outcomes. The *current protocol* is a necessary feasibility study to inform preliminary outcomes, design, and sample size for the future trial.

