### Aim 1: Part 2: Feasibility in clinical practice

There is a designated RSA at MSK and HH who will be responsible for recruitment, enrollment, data collection and study management at their respective site.

*Head and neck cancer survivors.* We will recruit an additional 45 survivors (30 from MSK and 15 from HH) to participate in Aim 1: Part 2 for feasibility testing. Patients who are eligible, scheduled, or due to be seen at the survivorship clinic at MSK and HH will be invited by mail to participate in the HN-STAR study. The patient will be able to opt out of the study by contacting the RSA. If the patient does not opt out, research staff at MSK or HH will follow-up with a phone call. At least three attempts will be made to reach the patient by phone. When the consenting professional at the respective site reaches the patient by phone, she will describe the study and invite interested and eligible patients to participate. The consenting professional will follow a standard consent script as described above. Patients will be consented over the phone with the RSA from their respective study site before completing the

Survivor Self-Assessment before the clinic visit. However, unlike Aim 1: Part 1, participants can complete the Survivor Self-Assessment online at home or in the waiting room before the clinic appointment.

Similar to Aim 1: Part 1, we will enrich for minorities in the MSK clinic by enrolling no more than 20 white non-Hispanic patients at MSK. After enrolling 20 white non-Hispanic patients from MSK, if we have not yet enrolled 30 total patients from MSK, we will only invite non-white or Hispanic patients to participate until 30 patients enroll. With over 20 new survivors seen in this clinic each month, this will not hinder enrollment.

At each study site, each study participant will receive \$50 from the RSA at their study site to provide thanks for their time and effort immediately following completion of the final study survey. This is less than the \$100 incentive for patients in Aim 1: Part 1 because the time and effort will be less for these participants.

*NP.* We will be asking the MSK and HH NP to provide feedback (via survey and interview) about their experience using HN-STAR. Through the consent process, participants will understand that their NP will be surveyed and interviewed about HN-STAR as part of the study. The NPs responsible for head and neck cancer survivors will be asked to provide written consent to participate.

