### **7.3 Passively Collected Data**

In addition to surveys, patient and nurse practitioner data will be recorded through the web interfaces of HN-STAR. In addition, NPs will document clinic notes as part of routine care. These data will be used to inform feasibility of HN-STAR and contribute to power calculations for the future multi-site randomized controlled trial.

**7.3.1** For all visits at MSK, preceding the patient visit, the NP will verify the Automated Treatment Checklist. When the NP makes any changes to imported data and verifies the final Treatment Checklist, these data will be collected. These data will inform the accuracy of the automatically generated treatment summary and the time required to verify the information.

**7.3.2** For all visits at HH, preceding the patient visit, the NP will complete the Manual Treatment Checklist. Data will be collected regarding the time required to complete the checklist.

**7.3.3** All patients will complete the Survivor Self-Assessment before their clinic visit. HN-STAR will record the amount of time taken, the items skipped, and the proportion of the Self-Assessment completed.

**7.3.4** As part of routine care, the NP will record topics addressed and actions taken in the clinic note for each visit. Clinic notes regarding the identification and management of late effects will be abstracted.

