### **7.4 Preliminary metrics for future trial**

Abstracted clinic note data and HN-STAR data will inform feasibility of data collection and assess preliminary outcomes for Aim 2.

**7.4.1** Clinic note data will be used as part of a pretest-posttest design, described in further detail in the Biostatistics section 11.3. At each clinic visit, the NP will record actions from the visit, including referrals, prescriptions, and other management plans in the clinic note as part of routine care. The RSA at each site will retrieve data regarding late effects identified and addressed in the year preceding the study visit and during the study visit, to assess changes before and after the HN-STAR intervention. The RSA will also assess

oncologic surveillance occurring in the year preceding the study visit and during the study visit from the medical record. RSAs will use the Medical Record Data Abstraction Form (Appendix H).

**7.4.2** The receipt of routine preventive care, including cancer screening tobacco cessation, immunizations, and routine general testing, is not routinely collected in the clinic note and will instead be collected from HN-STAR. We will only collect these outcomes once (before the HN-STAR visit), and they will not serve as outcomes for the pretest-posttest study.

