**Figure 4 continued. Outcome collection**

Assessment	Source	Timing (including end of data collection window)
Survivor Post-Visit Survey	Patient	Following clinic visit, before leaving clinic
Primary Care Provider Survey	PCP	At least one week after being mailed Survivorship Care Plan, within a month of enrollment into study
Passively collected feasibility metrics	HN-STAR	Immediate concurrent data collection via Webcore
Nurse Practitioner Interview	NP	After 30 patients have completed Aim 1: Part 2 at MSK and 15 patients have completed Aim 1: Part 2 at HH, within 1 month of last patient completing Aim 1: Part 2 at the respective site
Survivor Follow-up Interview	Patient	Six months after the clinic visit
Preliminary metrics for future trial (Aim 2)		
Oncologic metrics: Late effects identified and addressed, receipt of head and neck surveillance and appropriate follow-up (e.g. dental exam for those who underwent radiation therapy)	Clinic notes, prescriptions or referrals	Abstracted from any time in the year before the visit (pretest) and in the note pertaining to the clinic visit (posttest)
Non-oncologic metrics: Receipt of routine preventive care (e.g., cancer screening, tobacco cessation)	Survivor Self-Assessment	After completion of the Survivor Self-Assessment

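### The before-after difference meant for the future trial's power calculation compares a whole prior year of notes with one HN-STAR visit note

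*Combined protocol and SAP*

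**What the plan says.** Section 3.0 describes a future trial that randomizes clinics, in which "the primary outcomes will be changes in 1) the number of late effects identified and 2) the number of late effects managed in clinic". Under Section 2.0, the Aim 2 data are to "contribute to power calculations for the future trial".

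Section 7.4.1 has the research assistants retrieve "late effects identified and addressed in the year preceding the study visit and during the study visit", and applies the same two windows to oncologic surveillance. Figure 4 gives the timing of the oncologic metrics as "Abstracted from any time in the year before the visit (pretest) and in the note pertaining to the clinic visit (posttest"). The opening of 11.3 repeats those windows. The closing paragraph under 11.3.2 takes the before-after difference for the oncologic metrics, points back to Figure 4, and commits these differences to the power calculation of the randomized trial.

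On scale, 11.3.1 counts the late effects identified in each patient. For those addressed it says only: "We will then calculate the proportion of identified late effects that are addressed". Figure 4 and 11.3 mention late effects addressed without giving a scale. Appendix H, which 11.3 cites for the complete list, is not part of the supplied text.

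Nothing in the supplied text equalises the two windows or adjusts for the number of prior-year notes. No rule covers a patient with no prior note or with no late effect identified.

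**The concern.** The pretest asks whether a late effect was mentioned or addressed in any of a year's notes. The posttest asks the same of one note. With two or more prior notes the pretest has more opportunities, so its count tends to be higher even if care is unchanged. The difference then mixes any effect of HN-STAR with the length of the window. The surveillance elements, such as dental examination and thyroid studies, share the same windows.

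The stake is a planning input. A future sample size varies with the inverse square of the assumed difference, so a distorted difference carries straight through. If the sign is reversed, the figure is unusable.

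The scale question is secondary. HN-STAR is meant to raise identification (Section 3.0: "HN-STAR ensures the identification of all late effects by collecting symptom data directly from patients"), and identification is the proportion's denominator. A change in the proportion therefore cannot stand in for a change in the number.

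**Working it through.** The documents contain no power calculation, effect size or standard deviation to reproduce, and 11.1 says the study is not powered for formal tests. The structure comes from the text. **Every number in steps 1 to 4 is an assumption for illustration.**

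**1. Set-up.** Assume 10 late effects present, each note identifying 40% of them and addressing 75% of those identified. The chance that a given late effect is addressed in one note is 0.40 × 0.75 = 0.30. Let V be the number of prior-year notes and ρ the between-note correlation. With ρ = 0, P(never addressed in V notes) = 0.7^V. With ρ > 0, use a beta-binomial model with a = 0.3(1−ρ)/ρ and b = 0.7(1−ρ)/ρ. Then P(never addressed) is the product over j = 0 to V−1 of (b+j)/(a+b+j).

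**2. Number addressed, no HN-STAR effect.** The posttest expectation is 10 × 0.30 = 3.0. Pretest expectations at V = 3:
- ρ = 0: 10 × (1 − 0.343) = 6.57
- ρ = 0.5 (a = 0.3, b = 0.7): 10 × (1 − 0.7 × 0.85 × 0.9) = 4.65
- ρ = 0.8 (a = 0.075, b = 0.175): 10 × (1 − 0.7 × 0.94 × 0.967) = 3.64

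Posttest minus pretest:

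| Prior notes | ρ = 0 | ρ = 0.5 | ρ = 0.8 |
|---|---|---|---|
| 0 (scored as zero) | +3.0 | +3.0 | +3.0 |
| 1 | 0 | 0 | 0 |
| 2 | -2.10 | -1.05 | -0.42 |
| 3 | -3.57 | -1.65 | -0.64 |
| 4 | -4.60 | -2.05 | -0.79 |

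The average depends on the mix of patients. If half have no prior note and half have three at ρ = 0.5, it is 0.5 × 3.0 + 0.5 × (−1.65) = +0.68.

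**3. With a true effect.** If the HN-STAR visit identifies 60%, the posttest is 10 × 0.60 × 0.75 = 4.5 and the like-for-like gain is 4.5 − 3.0 = +1.5. Against three prior notes the plan's difference is −2.07, −0.15 or +0.86 for ρ = 0, 0.5 or 0.8.

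**4. Other metrics in the same model at V = 3, no effect.** The number identified changes by −3.84, −1.84 or −0.73 (for ρ = 0: 4.0 − 10 × (1 − 0.6³) = 4.0 − 7.84). The proportion addressed, as a ratio of totals, is 83.8%, 79.5% or 77.0% at pretest against 75.0% at posttest. Both scales are affected, the counts more.

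A simpler model (8 late effects, independent notes, chance of mention 0.3 to 0.7) gives the same direction for the number identified: 0 with one prior note, −1.7 to −2.0 with two, and −2.2 to −3.0 with three.

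**5. What a distorted difference does to a sample size.** With an assumed SD of 2, two-sided 5% level, 80% power and no clustering, n per arm = 2(1.96 + 0.84)² × 2²/δ². This gives 25 at δ = 1.6, 99 at 0.8 and 393 at 0.4.

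**6. Scale (minor point).** A patient going from 3 of 4 to 5 of 8 addressed gains 5 − 3 = +2 in number but changes by 5/8 − 3/4 = −12.5 percentage points in proportion. The proportion is undefined when none is identified. Under an assumed Poisson count with mean 4 (the per-note figure in step 1), that is 45 × e^−4 ≈ 1 patient of 45. It would be about 6 at mean 2 and 17 at mean 1.

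**The case against.** This is an unpowered feasibility study, and none of the feasibility criteria in 11.2 uses these metrics. That stands: the consequence falls on planning the next trial. Informing that planning is, however, a stated purpose of Aim 2.

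A reader might infer that the difference must be biased against HN-STAR, or that its sign will be reversed. The documents do not support that, because the number of prior notes and their overlap are not given. The bias is about zero with one comparable prior note and upward with none. Section 6.0 ("With over 20 new survivors seen in this clinic each month") suggests that some patients will lack an earlier note from the same clinic.

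A reader might also infer that the raw difference will be the assumed effect size. The text says only that differences will be used in, or contribute to, the calculation. It does not exclude that use or say what else would serve.

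On scale, a reader might infer that the number addressed is lost. It is not: it is the proportion's numerator, held for each patient, and a difference in that number is unnamed but not ruled out. Equating *addressed* with *managed* is also an inference. Section 7.3.4 supports it ("Clinic notes regarding the identification and management of late effects will be abstracted"), but 11.3.1 counts acknowledged inaction as addressed and Section 3.0 does not define managed.

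**Conclusion.** The concern holds in conditional form. The unequal windows are stated consistently in three places, and the resulting difference is committed to the power calculation. Followed as written, the plan can produce a difference driven by window length. In the illustration with three prior notes and no effect, the number addressed changes by −3.6 to −0.6, and a like-for-like gain of +1.5 appears as anything from −2.1 to +0.9. These sizes rest wholly on assumed inputs. The direction for patients with more than one prior note does not depend on the exact values, provided those notes are comparable with the visit note and not complete repeats of one another.

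The proportion-versus-number point is a minor gap in the named summaries. Both should be corrected, but neither affects this study's feasibility conclusions.

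**What to change.** **1. Windows.** In 7.4.1 and Appendix H, record the note from which each late effect identified or addressed was taken. In the closing paragraph of 11.3.2, let the power calculation draw on a like-for-like difference: the most recent comparable prior visit note against the HN-STAR visit note. Report its mean, the SD of the change and the number of patients who have such a prior note. Keep the year-versus-visit difference as description only, with the unequal windows stated, and do not use it as an effect size. Apply the same restriction to the surveillance elements. If few patients have a comparable prior note, supply only the visit-level mean and SD, and take the effect size from a stated target difference.

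**2. Scale.** In 11.3.1, also count the late effects addressed per patient (zero if none identified), with mean, SD and change. Keep the proportion as a secondary description, with the number of patients for whom it is undefined. State whether *addressed*, which includes acknowledged inaction, is the same outcome as *managed* in Section 3.0.

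**Cost.** Item 2 is wording only. Item 1 adds one field to abstraction already planned; the posttest is already a single note. The main downside is that the matched subset may be small and some prior notes may come from other providers. The between-clinic correlation that a clinic-randomized trial also needs is a separate input, which this change does not supply.
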